3.4. Treatment Adherence Rate and Extent of Exposure

Treatment adherence will be defined as: (number of capsules taken) / (number of capsules expected to be taken) * 100. When a subject discontinues treatment early, the number of capsules that should have been taken is based upon the duration the subject was on treatment.

Total number of days the subject is on study drug will also be summarized as a continuous variable and categorized into 12-week intervals. Days on study drug will be calculated as the number of days from date of first dose to date of last dose plus 1.

[figure not shown]
Treatment adherence and exposure will be summarized by enrollment group and overall. Supportive listings will be provided.

3.5. Efficacy Analyses

3.5.1. General Considerations

All efficacy analyses will be carried out using the FAS population. For rollover subjects, efficacy assessment in the antecedent ALK8700-A302 study will be carried over as baseline if visit 2 in current study is not collected. All efficacy endpoints will be summarized by enrollment group and overall. Supportive listings will be provided.

[REDACTED]

3.5.3. Clinical endpoints

- The change from baseline in the EDSS score
- Proportion of subjects experiencing a relapse at Week 96
- Annualized Relapse Rate (ARR) at Week 96
- Time to onset of 12-week confirmed disability progression
- Change in 25-Foot Walk from Baseline
- Proportion of subjects with No Evidence of Disease Activity (NEDA) at Week 96

EDSS Score

The EDSS is used to measure and evaluate MS patients' level of functioning. The EDSS provides a total score on a scale that ranges from 0 to 10. The first levels 1.0 to 4.5 refer to people with a high degree of ambulatory ability and the subsequent levels 5.0 to 9.5 refer to the loss of ambulatory ability. The range of main categories include (0) = normal neurologic exam; to (5) = ambulatory without aid or rest for 200 meters; disability severe enough to impair full daily activities; to (10) = death due to MS. In addition, it also provides eight subscale measurements called Functional System (FS) scores: pyramidal (motor function); cerebellar; brainstem, sensory; bowel and bladder; visual, cerebral or mental; and other. The Functional Systems (FS) are scored on a scale of 0 (low level of problems) to 5 (high level of problems) to best reflect the level of disability observed clinically. The total EDSS score is determined by two factors- gait and FS scores. EDSS scores below 4.0 are determined by the FS scores alone. EDSS scores between 4.0 and 9.5 are determined by both gait abilities and FS scores. For this study, the fatigue score should be recorded but not included in the calculation of the cerebral FS score.

The EDSS score and change from baseline during the Treatment Period will be summarized by enrollment group and overall.

Relapse

A protocol-defined relapse consists of the following:

- New or recurrent neurologic symptoms, not associated with fever or infection, lasting for at least 24 hours, accompanied by one or more of the following:
 - New objective neurological findings upon examination by the treating neurologist that are functionally consistent with findings on the EDSS (performed within

7 days of onset of symptoms) with an increase over the prior visit of ≥ 0.5 for the total score,

- An increase of ≥ 2 in one FS subscale scores and/or
- An increase of ≥ 1 in two FS subscale scores, except bladder/cognitive changes.

New or recurrent neurologic symptoms that evolve gradually over months should be considered disability progression, not an acute relapse. New or recurrent neurologic symptoms that occur less than 30 days following the onset of a protocol-defined relapse will be considered part of the same relapse, i.e., if 2 relapses have onset days that are ≤ 29 days of one another, they will be counted only as 1 relapse, and the onset date used in the analysis will be the onset date of the first relapse.

Assessment regarding protocol defined relapses will be summarized as frequency of relapses per subjects (0, 1, 2, 3, ≥ 4); along with estimated proportion of subjects experiencing a relapse at Week 96, which will be calculated with the use of the Kaplan–Meier product-limit method.

Annualized Relapse Rate

The annualized relapse rate for each enrollment group will be calculated as the total number of relapses experienced in the group divided by the total number of patient-years on study. In addition, the relapse rate for an individual patient will be calculated as the number of relapses for that patient divided by the number of patient-years followed. Based on these individual relapse rates, the mean and median for each enrollment group will be presented.

Time to Onset of 12-week Confirmed Disability Progression

The time to onset of 12-week confirmed disability progression is defined as the time from baseline to the first disability progression that is confirmed at the next regularly scheduled visit ≥ 12 weeks after the initial disability progression.

Disability progression is defined by one of the following:

- an EDSS increase of at least 1.5 points from baseline EDSS = 0
- an EDSS increase of at least a 1.0 point from baseline EDSS between 1.0 and 5.5 (inclusive), or
- an EDSS increase of at least 0.5 points from baseline EDSS = 6.0.

The date of the initial EDSS assessment at which the minimum increase in the EDSS is met will be the date of onset of the progression (tentative progression). The progression is defined as confirmed when this minimum EDSS change is present on the next study visit occurring after 12 weeks or longer from the onset of the progression. EDSS assessments within 30 days after a protocol-defined relapse will not be used for confirmation of disability progression. If a subject meets the defined criteria of confirmed progression and is also having a relapse, the subject will be required to meet the defined minimum criteria at the subsequent visit.

Death due to MS before a confirmed disability progression will be counted as progression. If the subject was in the midst of a tentative progression at the time of death (e.g. the EDSS evaluation prior to death is a tentative progression), the progression date will be the date of the onset of the progression. Otherwise, the progression date will be the date of death.

Subjects who do not have a confirmed progression based on the above rules will be censored. The censor date will be the date of the last EDSS assessment in the study, unless the subject was in the midst of a tentative progression. For subjects with a tentative progression at the last study visit, the censor date will be the date of the onset of the progression. Subjects who withdraw from the study after the baseline visit but prior to the first clinical evaluation scheduled visit will be censored at baseline.

Estimated proportion of subjects with 12-week confirmed progression at 48, 60, 72, 84, and 96 weeks will be calculated with the use of the Kaplan–Meier product-limit method and reported by enrollment group and overall.

Timed 25-foot walk (T25-FW) score

The T25-FW is a reliable quantitative mobility and leg function performance test based on a timed 25-foot walk (T25-FW). The subject is directed to one end of a clearly marked 25-foot course and is instructed to walk 25 feet as quickly as possible, but safely. Subjects are allowed to use assistive devices (canes, crutches, walkers) as needed. The time is calculated from when the lead foot crosses the start point to when the subject has reached the 25-foot mark. The task is immediately administered again by having the subject walk back the same distance. The score for the T25-FW is the average of the two completed trials.

The T25-FW score and change from baseline during the Treatment Period will be summarized by enrollment group and overall.

No Evidence of Disease Activity (NEDA)

Both NEDA-3 and NEDA-4 definitions will be used to identify subjects with NEDA. The definition of NEDA-3 encompasses a combination of three related measures of disease activity: no relapses, no confirmed disability progression sustained for 12 weeks as measured on EDSS and no MRI disease activity, defined as no new GdE lesions and no new or enlarging T2 hyperintense lesions. The definition of NEDA-4 is the above definition of NEDA-3 with the addition of a mean annualized rate of brain volume loss (AR-BVL) of less than 0.4% where AR-BVL is derived from percentage brain volume change from baseline (PBVC) and is calculated as $((\text{PBVC}/100+1)^{(365.25/\text{days})}-1)*100$ [2].

Proportion of Subjects with NEDA-3 and NEDA-4 at Week 96 will be summarized by enrollment group and overall. Estimated proportion of subjects with NEDA-3 and NEDA-4 at week 96 will be estimated using Kaplan-Meier product-limit method and reported by enrollment group and overall.

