### 7.2.2.      **Relapse**

Efficacy analyses related to MS relapse include only events of protocol-defined relapse. Protocol-defined relapse consists of the following:

- New or recurrent neurologic symptoms, not associated with fever or infection, lasting for at least 24 hours, accompanied by one or more of the following:

CONFIDENTIAL

The information contained herein may not be used, disclosed, or published without the written consent of Biogen MA Inc.

- New objective neurological findings upon examination by the treating neurologist that are functionally consistent with findings on the EDSS (performed within 7 days of onset of symptoms) with an increase over the prior visit of  $\geq 0.5$  for the total score,
- An increase of  $\geq 2$  in 1 functional system (FS), except bladder/cognitive changes, and/or,
- An increase of  $\geq 1$  in 2 FS, except bladder/cognitive changes.

New or recurrent neurologic symptoms that evolve gradually over months should be considered disability progression, not an acute relapse, and should not be treated with corticosteroids. New or recurrent neurologic symptoms that occur less than 30 days following the onset of a protocol defined relapse should be considered part of the same relapse and would not be treated with oral or IV methylprednisolone within the protocol.

- Subjects who experience new neurologic symptoms must contact the treating nurse or neurologist within 48-72 hours of the onset of symptoms to determine the necessity of an Unscheduled Relapse Visit (see Section 5.4).
- If required, the subject will then be evaluated in person by the neurologist *as early as possible* but within 7 days of the onset of the potential relapse.
- The neurologist is to perform a relapse assessment and obtain an EDSS score. New objective findings on neurological examination performed by the neurologist in conjunction with the EDSS changes described above will confirm whether the suspected protocol-defined relapse has occurred.
- Treatment of the acute event may then proceed at the discretion of the neurologist (according to the methylprednisolone regimen described in Section 7.2.1) only after the neurologist has completed his/her examination. Treatment of an acute event of relapse with oral or IV methylprednisolone will not affect the subject's eligibility to continue in the study.

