#### Other endpoints

- SF-12 (domain score)
- EQ-5D-5L VAS scores

The ARR will be summarized as number of relapses per subject per year, in which subject study duration is calculated as the time from first dose to last dose of study medication +1. NEDA will indicate an absence of select clinical (MS relapse and disease progression) [REDACTED] outcomes.

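### The SAP's copy of the protocol-defined relapse drops the bladder/cognitive exclusion from the one-functional-system line; its two ARR person-time terms also need aligning with the protocol

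*SAP*

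**What the plan says.** **Relapse.** SAP 3.5.3 opens its criteria with "A protocol-defined relapse consists of the following". The lead-in requires neurological symptoms that last 24 hours or more without fever or infection, together with at least one of three findings. The second finding is "An increase of ≥ 2 in one FS subscale scores and/or". The third is a rise of 1 point or more in two systems, and only there does the SAP exclude bladder and cognitive changes.

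Protocol 7.2.2 has the same lead-in and the same three findings, but its one-system line reads "in 1 functional system (FS), except bladder/cognitive changes, and/or", and its two-system line repeats the exclusion. The same section states: "Efficacy analyses related to MS relapse include only events of protocol-defined relapse". It also says that objective findings on the neurologist's examination "in conjunction with the EDSS changes described above will confirm whether the suspected protocol-defined relapse has occurred".

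**ARR.** Protocol 12.4 (Other endpoints) says that "subject study duration is calculated as the time from first dose to last dose of study medication +1". In SAP 3.5.3 the group rate is "calculated as the total number of relapses experienced in the group divided by the total number of patient-years on study", while each patient's own rate is that patient's relapses "divided by the number of patient-years followed". The SAP defines neither term. SAP 3.4 defines the first-to-last-dose interval plus 1 as days on study drug, for the exposure summary, and the ARR text does not refer to it.

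**Declared changes.** SAP section 5 lists only COVID-19 assessments.

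**The concern.** The SAP presents its list as the protocol's definition, yet one line is wider than the protocol's. The definition has real work to do. Protocol 11.3.1 records every MS relapse as an adverse event, whether or not it meets the protocol definition, so the analysis must separate the two kinds. The definition feeds the ARR, the Kaplan-Meier relapse proportion, NEDA-3 and NEDA-4, and the rule that EDSS assessments within 30 days after a relapse cannot confirm progression.

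The ARR denominator is a separate and weaker point. The SAP uses different words for the group and individual rates, defines neither, and does not point to the interval that the protocol fixes. The mean of individual rates is the summary most sensitive to this, because short exposures weigh most in it.

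**Working it through.** **1. The criteria side by side**

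| Finding that completes a relapse | Protocol 7.2.2 | SAP 3.5.3 |
|---|---|---|
| Objective findings with total EDSS up by 0.5 or more | yes | yes |
| One FS up by 2 or more | yes, bladder/cognitive excluded | yes, no exclusion on this line |
| Two FS up by 1 or more | yes, bladder/cognitive excluded | yes, bladder/cognitive excluded |

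The lead-in symptoms are required in both. An event falls under one definition only if all of these hold: the symptoms qualify; the bladder or cognitive FS rises by 2 or more; no other FS change qualifies; and the total EDSS rises by less than 0.5. Such an event is a relapse under the SAP lines and not under the protocol lines.

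**2. Direction and size.** The SAP wording only removes an exclusion, so every protocol relapse is also a SAP relapse. An added event is either counted or merged with a neighbour under the 30-day rule; it cannot remove one. The relapse count, and hence the ARR for a given person-time, is equal or higher. The documents give no frequency of isolated bladder or cognitive changes, so the size cannot be computed. The case is narrow: both documents say that EDSS scores below 4.0 depend on FS scores alone, so a 2-point FS rise may also lift the total by 0.5 and qualify under both.

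**3. ARR denominator.** Neither document states an ARR, so there is no figure to reproduce. Inputs from the visit schedules: Visit 15 on Day 673 and Visit 16 on Day 687, which is 14 days later. Assumptions: a completer's last dose is on Day 673; an early discontinuer is followed for 14 days after the last dose; the number of relapses is the same under both intervals.

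Rate = relapses × 365.25 / days. For last dose on Day d, the relative change on moving from d to d + 14 days is d/(d + 14) − 1.

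| Last dose (day) | d/(d + 14) | Change in individual rate |
|---|---|---|
| 673 | 673/687 = 0.980 | −2.0% |
| 337 | 337/351 = 0.960 | −4.0% |
| 169 | 169/183 = 0.923 | −7.7% |
| 57 | 57/71 = 0.803 | −19.7% |

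With one relapse and last dose on Day 57, the rate is 365.25/57 = 6.41 per year against 365.25/71 = 5.14.

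For the group rate, if nobody stops early the change is −2.0%. If 30% are assumed to stop at Day 84, mean days are 0.3 × 84 + 0.7 × 673 = 496.3 against 510.3. The ratio is 0.973, a change of −2.7%. If the SAP terms already mean first dose to last dose plus 1, every change in this step is zero.

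**The case against.** **On relapse.** The omission looks like a copying slip. The SAP says it is based on protocol version 5.0, labels the event protocol-defined, and describes no algorithm for deriving relapses from FS scores. FS scores alone could not produce the event, since symptoms are also required. The exclusion at the end of the last line may have been meant for both FS lines. If the analysis counts the neurologist's confirmation, made under the protocol wording, no count changes. All of this stands as a limit on the effect. It does not make the SAP line correct, and the SAP does not say which source of relapses it counts.

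A reader might infer that the SAP deliberately widened the endpoint, or that the reported ARR will be inflated. The documents support neither. They show a mismatch in wording whose effect may be nil.

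**On ARR.** A reader might infer that the SAP replaced the protocol's denominator. That is not shown. The protocol itself calls the dosing interval the subject's study duration, so person-time on study can naturally mean the same thing, and an SAP that does not restate a protocol definition has not thereby changed it. Against this, SAP 3.1.2 counts completion of the study as treatment plus follow-up, so a longer reading is also open. SAP sections 6 and 8 place dataset and programming specifications in separate documents, which may settle the derivation. It therefore cannot be claimed that programmers would in fact reach different answers.

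The percentages are conditional on time running to Visit 16, which no section names as the ARR denominator, and on no added relapses. The 19.7% belongs to a single early discontinuer; the group rate moves by about 2% to 3%, and the SAP also reports the median of individual rates.

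**Conclusion.** The relapse point holds as a wording error. The SAP's one-system line admits events that the protocol excludes, under a label saying the two definitions are the same, with no declared change. Its direction is known (equal or more relapses) and its size is not. It is zero if confirmed relapses under the protocol definition are counted, or if the trailing exclusion is applied to both lines.

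The ARR point is a matter of alignment: two undefined terms that differ from each other, not a demonstrated departure.

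The efficacy endpoints are exploratory (Protocol 9.1 and 12.2.2) and summarized descriptively (Protocol 12.4), in an open-label safety study with no formal sample size calculation. No test, error rate or decision depends on either point. This is a minor correction.

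**What to change.** 1. In SAP 3.5.3, put the bladder/cognitive exclusion on the one-system line so that the list matches Protocol 7.2.2, and state that the analyses count relapses confirmed under that definition.
2. For both the group and the individual ARR, replace the two person-time terms with days on study drug (SAP 3.4) divided by 365.25, which is the protocol's first dose to last dose plus 1. If a different interval is intended, define it and declare it in SAP section 5.
3. State whether relapses after the last dose count in the numerator. Neither document restricts relapse onset to the dosing interval, so this is the sponsor's choice; it should be consistent with the denominator.

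The cost is a few lines of SAP text. No new data are needed, and the dosing interval is already derived for the exposure table. If item 3 leads to an onset window, applying it is a small programming step.

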#### 6.1.2. De Novo Subjects

In order to qualify for participation in this study, De Novo Subjects must meet all of the following criteria:

1. Is willing and able to provide informed consent.
2. Capable of understanding and complying with the protocol.
3. Agrees to use an acceptable method of contraception for the duration of the study and for 30 days after any study treatment administration or is surgically sterile or postmenopausal (see [Section 11.5](#)).
4. Male and female adults aged 18 to 65 years, inclusive, at screening.
5. Has a confirmed diagnosis of RRMS according to the revised 2010 McDonald criteria [[Polman 2011](#)].
6. EDSS score of 0.0-6.0 at screening and Visit 2.
7. Neurologically stable with no evidence of relapse within 30 days prior to Visit 2.

CONFIDENTIAL

The information contained herein may not be used, disclosed, or published without the written consent of Biogen MA Inc.

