### **9.1.3. Timed 25-Foot Walk**

The T25-FW [\[Kaufman 2000\]](#) is a reliable quantitative mobility and leg function performance test based on a timed 25-foot walk. The subject is directed to one end of a clearly marked 25-foot course and is instructed to walk 25 feet as quickly as possible, but safely. Subjects are allowed to use assistive devices (canes, crutches, walkers) as needed. The time is calculated from when the lead foot crosses the start point to when the subject has reached the 25-foot mark. The task is immediately administered again by having the subject walk back the same distance. The score for the T25-FW is the average of the 2 completed trials.

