### **12.1. General Considerations**

The statistical analysis methods are described below. Additional details will be provided in the Statistical Analysis Plan.

In general, summary statistics (number of subjects, mean, standard deviation, median, minimum, and maximum values for continuous variables, and number and percentage of subjects in each category for categorical variables) will be provided for all parameters. All statistical results will be presented based on observed values. All individual subject level data will be presented as data listings.

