7. GENERAL STATISTICAL METHODOLOGY

In general, summary statistics (n, mean, SD, median, minimum, and maximum for continuous variables, and number and percentage of subjects in each category for categorical variables) will be provided by treatment group. All summary tables will be based on observed data, and missing values will not be imputed unless otherwise indicated. Measurements collected from unscheduled visits or repeated assessments will not be included in the by-visit summary tables or figures, but will be included in the derivation of the last post-baseline value during treatment, the analyses for the potentially clinically significant (PCS) post-baseline values, and subject listings. Source data for the summary tables and statistical analyses will be presented as subject data listings.

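### The timed 25-foot walk has no rule for subjects who cannot complete it, so they leave the mean change, which then looks better than it is by an unknown amount (minor)

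*SAP*

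**What the plan says.** - **Score.** SAP section 3.5.3: "The score for the T25-FW is the average of the two completed trials". Protocol section 9.1.3 has the same rule: "The score for the T25-FW is the average of the 2 completed trials".
- **Analysis.** SAP section 3.5.3: "The T25-FW score and change from baseline during the Treatment Period will be summarized by enrollment group and overall". SAP section 7 gives the default statistics for a continuous variable: n, mean, SD, median, minimum and maximum. No worsening category is planned for T25-FW.
- **Missing data.** SAP section 7: "All summary tables will be based on observed data, and missing values will not be imputed unless otherwise indicated". Protocol section 12.1: "All statistical results will be presented based on observed values". Nothing different is indicated for T25-FW.
- **Who can be affected.** De Novo entry requires "EDSS score of 0.0-6.0 at screening and Visit 2". The Rollover criteria in protocol section 6.1.1 set no EDSS limit. SAP section 3.5.3 also says "Subjects are allowed to use assistive devices (canes, crutches, walkers) as needed".
- **Status.** Protocol section 9.1 describes the assessment of treatment effect over time, T25-FW included, as exploratory. SAP section 3.5.3 lists change in the walk among the clinical endpoints.

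Neither document gives a maximum time, a worst rank, a category or count for inability to walk, or a score for a subject who completes only one of the two trials.

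**The concern.** For a timed walk, failing to finish can itself be the worst result. If the score exists only for completed trials and missing scores are left out, the subjects who have declined most contribute nothing to the change from baseline at that visit. The missingness is caused by the quantity being measured, so the error has one direction: the mean change is too favourable.

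The study has no control arm, so the reported change is itself the result, and there is no between-arm comparison in which a similar loss might partly cancel. The planned n does not expose the problem either. A falling n mixes inability with withdrawal and missed visits, and SAP section 3.8 acknowledges data collection difficulties during COVID-19.

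**Working it through.** The documents state no T25-FW mean, SD, effect size or expected number unable to walk, so there is no planned figure to reproduce. The check has three steps.

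**1. Apply the written rules to a subject who attends but cannot finish the course.** There are not two completed trials, so there is no score (SAP 3.5.3). No score means no change from baseline. Missing values are not imputed (SAP 7). The subject is therefore outside that visit's mean, SD and median.

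**2. Size of the effect on the mean.** All inputs are assumptions:
- q = share of subjects assessed at the visit who cannot complete the walk (0.5% to 5%, or 5 to 50 per 1000)
- D = change from baseline assigned to such a subject (10, 30 or 60 s)
- c = mean change among completers (0 s)

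Mean change with everyone counted = (1 − q) × c + q × D. The planned mean is c. The difference, by which the planned mean understates worsening, is q × (D − c).

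| q | D = 10 s | D = 30 s | D = 60 s |
|---|---|---|---|
| 0.5% | 0.05 s | 0.15 s | 0.30 s |
| 1% | 0.10 s | 0.30 s | 0.60 s |
| 2% | 0.20 s | 0.60 s | 1.20 s |
| 5% | 0.50 s | 1.50 s | 3.00 s |

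For example, 0.02 × (60 − 0) = 1.20 s. With c = 0.3 s the range hardly changes: 0.005 × 9.7 = 0.0485 s up to 0.05 × 59.7 = 2.985 s. Under the plan the reported mean is c in every cell.

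**3. How the mean, median and a worsening proportion respond.** This was simulated with 1000 subjects and 300 runs. Assumptions: median baseline 6 s (log-normal, log-scale SD 0.35), change with mean 0 and SD 1 s, slower walkers more likely to become unable, and a time of 60 s given to those unable. Each cell shows completers only → everyone counted.

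| q | Mean change | Median change | Share worsening by at least 20% |
|---|---|---|---|
| 2% | 0.003 → 1.021 s | 0.003 → 0.029 s | 12.3% → 14.0% |
| 5% | 0.000 → 2.553 s | 0.000 → 0.066 s | 12.4% → 16.8% |

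The mean depends heavily on the time assigned. The median does not: it needs only that those unable rank as worst. About 12% cross the 20% line with no mean change at all, so an unconfirmed per-visit proportion of this kind mostly reflects variability under these assumptions.

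**The case against.** The other side has several fair points.

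- **Exclusion is inferred from silence.** The scoring sentence closes a description of how the test is given; it is not an explicit rule for failed walks. Dataset and programming specifications are separate documents (SAP sections 6 and 8), and the protocol's amendment history mentions an administration and scoring manual for the test. Any of these could hold a rule. This stands as a limit on what can be asserted, but a rule on how the worst outcome counts belongs in the SAP.
- **EDSS already captures lost walking.** This is largely true. SAP Table 1 schedules EDSS at the treatment-period visits that have T25-FW, and loss of ambulation enters EDSS change, 12-week confirmed progression and, through that, NEDA. Confirmation needs a later visit, however: under SAP 3.5.3 a tentative progression at the last visit is censored. EDSS also does not alter the T25-FW summary.
- **n, the median and listings are planned.** The listings may allow missing walks to be traced. The planned median omits the same subjects as the mean, so giving it prominence would not repair the summary.
- **Few subjects may be affected.** Assistive devices are allowed, and the documents give no expected number.

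A reader might infer more than the documents support:

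- **That group walking speed will look stable.** Subjects who slow down but still finish stay in the mean, so it can worsen.
- **That the bias grows at later visits.** This is plausible but not shown.
- **That the study cannot report how many subjects worsened on walking.** This is too strong, given the listings and EDSS.
- **That the bias is several seconds.** A long cap produces such figures: 180 s against a typical 6 s gives 0.02 × 174 = 3.48 s at 2% unable. Neither time is in the documents, and the result mainly reflects the penalty chosen.

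**Conclusion.** The point holds in a limited form. Under the written rules, a subject unable to complete the walk because of MS has no T25-FW score and drops out of that visit's change from baseline, which makes the mean change look better than it is. The direction is clear if c is below D. The amount is not determined by the documents: 0.05 to 3.0 s over the assumed ranges above, and towards the lower end if assistive devices keep q small. The conclusion also assumes that no unseen specification already supplies a rule.

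Severity is minor. The endpoint is exploratory and descriptive, in an open-label safety study with no formal sample size calculation, and neither document attaches a test or decision to it.

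**What to change.** In SAP section 3.5.3, under the T25-FW score:

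1. Separate inability to complete because of MS from a walk not done for other reasons. Use the recorded reason or, where none was recorded, a data query, with the same-visit EDSS as support. State the score when only one trial is completed.
2. Report the number and percentage unable at each visit beside n.
3. Add a supplementary summary of change, by median and quartiles, that ranks those unable as the worst outcome. No time has to be invented.

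A worsening proportion that counts inability as worsened is optional. The documents give no threshold, so the sponsor should prespecify and justify one, and should say whether worsening must be confirmed at a later visit.

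The cost is one extra table, one derivation rule and a few data queries. The documents do not show whether the case report form records why a walk was not completed, so the number of queries depends on that. The change covers subjects who attend and cannot finish; those who have withdrawn remain missing.
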